6.3.2 Serial Biopsies

At each time point described above, subject will have a biopsy obtained (up to 3 cores), divided into a formalin fixed, paraffin embedded specimen and a fresh frozen specimen to be analyzed. Biopsy can be either needle biopsy or excisional biopsy, depending on the site of the tumor, according to physician's

preference. Tissue will be used for future studies, if subjects consent to tissues to be banked. See study procedure manual for shipping and other instructions. The purpose of the baseline pre-enzalutamide tumor tissue is to gather an understanding of ER+ breast cancers that may or may not benefit from AR signaling inhibition. The biopsy 4 weeks into treatment is taken at the time that both drugs are at their steady state concentrations (eg, following the loading doses of fulvestrant, and at least 4 half-lives of exposure to enzalutamide (T1/2 = 5.7 days). This will examine the subacute effects of this treatment on the tumor tissue, on AR and ER signaling. The purpose of the biopsy at time of progression is to obtain insights as to the mechanism of resistance to this treatment. We expect about half the patients to allow us to do this biopsy (based on previous experience).

7. RISKS AND BENEFITS:

7.1 Risks of This Protocol

- Clinical toxicities of fulvestrant (standard agent) plus enzalutamide as outlined in package insert and investigator brochure.
- Biopsies (each one is requested of the patient).
- Misuse or inadvertent release of information.
- Identification of the patient by release of comprehensive genomic information.
 - Pharmacogenomic analysis typically does not identify a genetic predisposition to a disease since its analysis typically is restricted to enzymes that metabolize the therapeutically administered agents.
- Low white blood cell count, which may increase risk of infection.
- Blood clot in the lungs (also known as pulmonary embolism).

7.2 Knowledge to Be Gained

- The relationship between the clinical efficacy measures (response, clinical benefit rate, PFS) and AR signaling will be examined.
- Characteristics of breast cancers that are resistant to enzalutamide with or without other targeted agents. A set of putative biomarkers will be identified.
- Mechanisms of resistance to enzalutamide-based treatment that arise in the clinic.

7.3 Justification of Risks

The clinical impact of enzalutamide in breast cancer is not yet determined. If the tumor appears to progress, the patient can be taken off study and treated accordingly as per the treating physician.

The extent of AR expression that correlates with enzalutamide efficacy is unknown and is an objective of this study; therefore, all patients, including those with “AR-negative” breast cancer, will be enrolled to receive standard of care fulvestrant with enzalutamide.

The choice of this combination was to take advantage of the lack of PK interaction between the two agents and conduct a phase II trial.

8. ASSESSMENT OF SAFETY:

8.1 Serious Adverse Events

A serious adverse event or reaction is any untoward medical occurrence that at any dose:

- Results in death (death solely as a result of disease progression is not a serious adverse event);
- Is life threatening (i.e., the patient was at immediate risk of death at the time of the event). "Life threatening" does not include an event that hypothetically might have caused death if it were more severe. For example, drug induced hepatitis that resolved without evidence of hepatic failure would not be considered life threatening even though drug induced hepatitis can be fatal;
- Requires inpatient hospitalization or prolongation of existing hospitalization;
- Results in persistent or significant disability/incapacity (i.e., a substantial disruption of the patient's ability to carry out normal life functions);
- Is a congenital anomaly/birth defect;
- Is a medically important event, including seizure.

8.3 Adverse Events

- An adverse event is defined as any untoward medical occurrence in a patient or clinical investigation patient administered a pharmaceutical product and which does not necessarily have to have a causal relationship with study drug.
- An adverse event observed after starting administration of the study drug or comparator drug is called a “treatment-emergent adverse event.” Treatment-emergent adverse events will be analyzed and discussed in the clinical study report for this study.

8.4 Procedure in Case of Pregnancy

- The effect of enzalutamide in pregnant and lactating women is not known, and the exposure of a fetus or nursing infant is considered a potential risk. Enzalutamide can cause fetal harm when administered to a pregnant woman based on its mechanism of action. Subjects receiving enzalutamide are advised to use 2 acceptable methods of birth control (one of which must include a condom as a barrier method of contraception) starting at the time of screening for an enzalutamide study and continuing throughout the course of treatment and for at least three months after enzalutamide is discontinued.
- The Investigator should report the outcome of the pregnancy (independent of outcome, eg. full term delivery, pre-term delivery, spontaneous abortion, induced abortion, stillbirth, death of newborn, congenital anomaly [including anomaly in a

miscarried fetus, etc.] in accordance with the same reporting procedure as for SAEs. The date of outcome of the pregnancy, gestational age, date of birth and neonatal data etc., should be included in this information.

8.5 In Case of Injury

In the event of a side effect or injury, appropriate medical care as determined by the Investigator or his/her designated alternate will be provided. No other compensation of any type will be provided by the study Sponsor.

8.6 Safety Monitoring and Reporting

A monthly teleconference will be held amongst the institutional investigators to review patients and adverse events.

9. STUDY OVERSIGHT:

9.1 Data Safety and Monitoring Oversight

The sponsor investigator will be responsible for monitoring the trial per the trial monitoring plan, in addition to overseeing the safety and efficacy of the trial including any specimens collected, executing the data and safety monitoring (DSM) plan, and complying with all reporting requirements to local and federal authorities. This oversight will be accomplished through additional oversight from the Data and Safety Monitoring Committee (DSMC) at the University of Colorado Cancer Center (CU Cancer Center). The DSMC is responsible for ensuring data quality and study participant safety for all clinical studies at the CU Cancer Center, which is the coordinating institution of this trial.

A summary of the DSMC's activities is as follows:

- Conduct of internal audits
- Ongoing review of all serious adverse events (SAEs), unanticipated problems (UAPs) and reportable adverse events (AEs)
- Has the authority to close and/or suspend trials for safety or trial conduct issues
- May submit recommendations for corrective actions to the CU Cancer Center's Executive Committee

Per the CU Cancer Center Institutional DSM Plan, SAEs, UAPs and reportable AEs are reported to the DSMC, IRB and the sponsor investigator per protocol. All SAEs, UAPs and reportable AEs are to be reported to the DSMC within 5 business days of the sponsor investigator receiving notification of the occurrence.

Each subject's treatment outcomes will be discussed by the site PI and appropriate staff at regularly scheduled meetings. Data regarding number of subjects, significant toxicities, dose modifications, and treatment responses will be discussed and documented in the meeting's minutes.

The sponsor investigator is responsible for organizing and conducting regularly scheduled teleconferences with all participating sites. The sponsor investigator will also be responsible for including data from all of the participating sites to include the minutes from these regularly scheduled teleconferences between the sponsor investigator and the sites within the overall trial's six month DSM report.

The sponsor investigator will provide a DSM report to the CU Cancer Center DSMC on a six month basis. The DSM report will include a protocol summary; current enrollment numbers; summary of toxicity data to include specific SAEs, UAPs and AEs; any dose modifications; all protocol deviations; and protocol amendments. The DSM report submitted to the DSMC will also include, if applicable, the results of any efficacy data analysis conducted. Results and recommendations from the review of this six month report by the DSMC will then be provided to the sponsor investigator in a DSMC review letter. The sponsor investigator is then responsible for ensuring this letter is submitted to the site's IRB of record at the time of IRB continuing review.

9.3 Auditing

Independent audits will be conducted by the CU Cancer Center DSMC. Independent auditors from the sponsor investigator's authorized representative will be allowed by the site's PI. In addition, audits may be conducted at any time by appropriate regulatory authorities and/or the IRB. During the course of the study and after it has been

completed it is likely that 1 or more study site visits will be undertaken by authorized representatives of the Sponsor.

The purpose of the audit is to ensure that the study is being, or has been, conducted and monitored in compliance with the protocol as well as recognized cGCP guidelines and regulations, to ensure monitoring practices are performed consistently across all participating sites and that monitors are following the CMP, as defined herein. These audits will also increase the likelihood that the study data and all other study documentation can withstand a subsequent regulatory authority inspection.

If such audits are to occur, they will be arranged for a reasonable and agreed time.

All reports and patient samples will be identified only by the patient's ID number and the patient's initials in order to maintain patient confidentiality. Additional patient confidentiality issues are covered in the Clinical Trial Agreement and in the informed consent form signed by the patient.

10. STATISTICAL CONSIDERATIONS:

10.1 Clinical Data

Age, ethnicity, race, gender, breast cancer histology (ductal, lobular, other), breast cancer subtype (ER, PR, Her2, Ki67, AR), detailed prior treatment history, selected comorbidities (especially insulin, metformin use), clinical response, CBR, PFS at 12 weeks, TTP. Details of treatment, including AE, SAE, and compliance.

10.2 Sample Size

10.2.1 Determination of Sample Size

The primary outcome is the clinical benefit rate. Assuming the undesirable rate of 10% and desirable rate of 30%, a sample size of 24 provides 89% power to detect this 25% rate difference using an exact binomial test with a one-sided alpha of 0.085. If 5 or more patients show clinical benefit the drug combination warrants further evaluation. During treatment period, patients might withdraw due to toxicity or loss to follow-up before on treatment for 24 weeks. Table below summarize the statistical power and the decision rule for sample size from 24 to 20, a 20% loss in the total sample size, which is the upper bound for loss seen in practice.

Statistical Power	n	Actual Alpha	Reject H0 If R ≥
0.89	24	0.085	5
0.86	23	0.073	5
0.84	22	0.062	5
0.80	21	0.052	5
0.76	20	0.043	5

R is the response as the clinical benefit

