3.1 Study Design

[figure not shown]
Single arm, non-randomized, open-label treatment consisting of:

- Fulvestrant 500 mg IM given days 1, 15, 28, then every 4 weeks as per standard of care (SOC). Fulvestrant may have already been started.
- Enzalutamide 160 mg daily.

If pre- or perimenopausal, patients will also receive goserelin 3.6 mg sq every 4 weeks (or equivalent) as per standard of care (SOC).

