3.3 Study Periods

The study periods will be as follows for all patients:

- Screening: Up to 28 days before treatment;
- Treatment: Day 1 of treatment through discontinuation of enzalutamide treatment;
- Safety follow-up: Approximately 30 days after the last dose of enzalutamide or before initiation of a new antitumor treatment, whichever occurs first.

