4.1 Inclusion Criteria

1. ER+ Her2- breast cancer
2. Metastatic
3. Female, at least 18 years of age
4. Candidate for fulvestrant therapy – patients who have started fulvestrant may enter this trial if within 3 months of starting fulvestrant
5. Measurable or evaluable by RECIST 1.1

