6.1 Study Procedures

Study Phase	Screening	Treatment				Progression	Follow-up
		1	5	9	13 [1]		
Study Week	-4 to -1	1	5	9	13 [1]	varies	varies [10]
Window (Days)	28	n/a	+/- 7	+/- 7	+/- 7	n/a	+/- 7 days
Informed Consent	x						
Eligibility	x						
Medical History	x						
Archived Tissue Collection [2]	x						
Tumor Imaging [3]	x			x			
Physical Exam	x	x	x	x	x	x	
Adverse Events	x	x	x	x	x	x	x
Concomitant Medications	x	x	x	x	x	x	
Study Drug Dispensing [4]		x		x			
Fulvestrant [9]		x	x	x	x		
Tumor Biopsy		x [5]	x			optional	
Hematology, Serum Chemistry [6]	x	x [8]	x	x	x	x	
PT/INR, PTT [11]	x		x			x	
Urine Pregnancy Test [12]	x						
Circulating Tumor Biomarkers	x	x [8]	x	x	x	x	
CTCs [7]	x	x [8]	x	x		x	
Survival & Recurrence Follow-up							x

[1] Continue every 4 weeks until progression.

[2] From primary lesion and/or metastatic sites previously biopsied. If tissue is available, archival blocks from both sites (primary and metastatic) should be collected, however, the top priority is the primary tissue.

[3] Within approximately 28 days before study entry and includes CT with contrast (unless medically contraindicated) of chest, abdomen, and pelvis. Bone assessments as clinically indicated. Thereafter, perform assessments every 8 weeks up to week 49 and then every 12 weeks thereafter until progression is documented per RECIST 1.1 or permanent treatment discontinuation. MRI is acceptable if CT not possible. Use the same testing across time.

[4] Refill every 8 weeks as long as patient remains on active treatment.

[5] Before treatment, but after eligibility determined.

[6] Hematology: hematocrit, hemoglobin, platelet count, red blood cell count, total neutrophils (absolute), white blood cell count with differential. Chemistry: albumin, alkaline phosphatase, ALT (alanine aminotransferase), AST (aspartate transaminase), blood urea nitrogen and creatinine; Ca⁺⁺, Cl⁻, K⁺, Na⁺; glucose (non-fasting), total bilirubin, total CO₂ (bicarbonate), total protein.

[7] CTCs will be collected at all participating sites, coded to remove patient identifiers, and shipped to UCCC and USC for processing as outlined in the lab manual.

[8] Only one sample is needed pretreatment (either during screening or prior to treatment on C1D1).

[9] Given IM on days 1, 15, and 28 (C2D1), and then every 4 weeks as per standard of care (SOC).

[10] 30 days after the last dose of enzalutamide or before initiation of a new antitumor treatment, whichever occurs first. May be done by telephone.

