10.4.2 Analysis Methods

10.4.2.1 Summary Statistics

Summary statistics will be used for the primary outcome clinical benefit rate as well as the response rate. Clinical benefit rate is defined as the proportion of subjects with complete response or partial response or stable disease. Response rate is defined as the proportion of subjects with complete response or partial response. 95% exact confidence intervals will be provided. Kaplan-Meier product limit survival plots will be generated and median survival time and associated 95% CI will be estimated, the PFS percentage at 12 and 24 weeks will be calculated. Descriptive statistics will be used to summarize the safety data such as the DLT for both hematologic and non-hematologic toxicity per type and grade, as well as all collected AE data, which will be listed per patient, and cycle. For the biopsy samples, exploratory analyses such as multivariable logistic regression, linear regressions and survival analyses will be required to attempt to classify protein, gene, or TUNEL markers associated with clinical outcomes such as response, clinical benefit and PFS as predictive (of therapeutic impact) or prognostic (of intrinsic tumor

biology). Bio-informatics tools such as unsupervised pathway analysis will also be explored. The following molecular characteristics at baseline will be explored among others: 1) Nuclear to cytoplasmic localization of AR staining. 2) Strength of AR signaling as measured by the expression of downstream AR-regulated genes, which should reflect dependence of the tumor cell on AR function. 3) AR:ER ratio with resistance to anti-estrogen therapy.

The same summary statistics will be used for the response rate and clinical benefit rate. Response rate is defined as the proportion of subjects with complete response or partial response. Clinical benefit rate is defined as the proportion of subjects with complete response or partial response or stable disease. Kaplan-Meier product limit survival plots will be generated and median survival time and associated 95% CI will be estimated for each arm. Combined and separate data for patients with AR+ and AR- BC and those with one prior endocrine therapy and those with more than one prior endocrine therapy for metastatic breast cancer.

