10.5.2.3 Progression Free Survival

For all patients enrolled, PFS will be defined as the time from the first day of enzalutamide treatment (Study Day 1) until documented disease progression or death on study, whichever occurs first. For patients who do not die or experience disease progression on study, PFS will be right censored at the day of the last information available for progression assessment. Kaplan-Meier methods will be used to describe PFS by dose level and overall.

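### Does testing new fulvestrant starters together with patients already up to 3 months into fulvestrant undermine the 5-of-24 rule?

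*Combined protocol and SAP*

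**What the plan says.** Section 3.1 describes fulvestrant plus daily enzalutamide and adds: "Fulvestrant may have already been started". Inclusion criterion 4 in section 4.1 sets the limit: "patients who have started fulvestrant may enter this trial if within 3 months of starting fulvestrant". Sections 4.1 and 4.2 put no cap on this group and no condition on its disease course since fulvestrant began.

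Section 2.2 makes the clinical benefit rate of the combination the primary objective, with stable disease for 24 weeks counting as benefit. Section 10.2.1 gives one pair of rates for everyone, "Assuming the undesirable rate of 10% and desirable rate of 30" per cent, and one rule: "If 5 or more patients show clinical benefit the drug combination warrants further evaluation". The efficacy population in section 10.4.1 depends only on at least 4 weeks of enzalutamide.

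PFS is timed from the first enzalutamide dose (section 10.5.2.3), and the treatment period is "Day 1 of treatment through discontinuation of enzalutamide treatment" (section 3.3). Baseline imaging is "Within approximately 28 days before study entry" (section 6.1, note 3).

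The planned separate results in section 10.4.2.1 are: "Combined and separate data for patients with AR+ and AR- BC and those with one prior endocrine therapy", with more than one prior endocrine therapy as the other level. Fulvestrant status at entry is not among them. Detailed prior treatment history is collected (section 10.1), and patient data listings are planned (section 10.4).

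**The concern.** A patient who enters after some weeks on fulvestrant may have been selected by how she did on it. If she has passed the period of early progression, her chance of a further 24 weeks of stable disease could exceed that of a new starter, whatever enzalutamide adds. If enzalutamide is added because fulvestrant is failing, her chance could be lower. Imaging close to entry largely resets earlier shrinkage but does not undo selection for continued stability.

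A go needs only 5 patients with benefit. If most of them came from the already-started group, a reader might credit the combination with what fulvestrant had already achieved. If the 10% null did not fit that group, the stated error rate of 0.085 would seem to be wrong too. No prespecified table would show the clustering.

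**Working it through.** **Inputs.** n = 24, threshold 5, rates 10% and 30% (section 10.2.1). The number already on fulvestrant and their benefit rate are not in the documents. The values used for them below are assumptions.

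**1. The plan's own figures.** For X ~ Binomial(24, p):
- P(X ≥ 5 | p = 0.10) = 0.0851
- P(X ≥ 5 | p = 0.30) = 0.8889

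The table states 0.085 and 0.89, so both reproduce.

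**2. Mixed entry groups.** Let k patients already on fulvestrant have rate q, and 24 − k new starters have 10%. Then P(go) = P(Binomial(k, q) + Binomial(24 − k, 0.10) ≥ 5). The pooled rate is p̄ = [kq + (24 − k) × 0.10] / 24. The last column gives P(go) if all 24 patients had rate p̄.

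| k | q | p̄ | P(go), mixed | P(go), uniform p̄ |
|---|---|---|---|---|
| 6 | 20% | 12.5% | 0.171 | 0.173 |
| 12 | 5% | 7.5% | 0.030 | 0.030 |
| 12 | 15% | 12.5% | 0.172 | 0.173 |
| 12 | 20% | 15% | 0.285 | 0.287 |
| 18 | 20% | 17.5% | 0.414 | 0.414 |

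The last two columns agree to within 0.002. What moves P(go) is the pooled rate; mixing adds almost nothing. Where p̄ exceeds 10%, the null of section 10.2.1 is false, so a go in those rows is not a type I error.

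**3. Mixing with the null true.** Take 12 patients at 5% and 12 at 15%: p̄ = (12 × 0.05 + 12 × 0.15) / 24 = 0.10. P(go) = 0.082, against 0.085 for a uniform 10%. The reason is that unequal rates reduce the variance of the total:
- uniform: 24 × 0.10 × 0.90 = 2.16
- mixed: 12 × 0.05 × 0.95 + 12 × 0.15 × 0.85 = 0.57 + 1.53 = 2.10

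**4. Can a direction be derived?** Suppose 10% were progression-free 24 weeks after starting fulvestrant, with Weibull times and progression-free entry spread evenly over weeks 0 to 12. The mean 24-week rate from entry is then 7.0% / 10% / 15.9% / 23.3% for shape 1.3 / 1.0 / 0.7 / 0.5. A constant hazard gives no shift, a rising hazard lowers the rate and a falling hazard raises it. The documents support no particular shape, and they do not say that 10% is a fulvestrant-alone rate.

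**5. What a split could show.** Assume 12 patients per group and 5 with benefit. The number of ways to choose the 5 is C(24,5) = 42,504.
- P(4 in the already-started group) = C(12,4) × 12 / 42,504 = 5,940 / 42,504 = 0.140
- P(5 in that group) = C(12,5) / 42,504 = 792 / 42,504 = 0.019
- P(4 or 5) = 0.158 by chance alone
- Two-sided Fisher p: 4–1 gives 2 × 0.158 = 0.32; 5–0 gives 2 × 0.0186 = 0.037
- Exact 95% intervals: 4/12 gives 9.9% to 65.1%; 1/12 gives 0.2% to 38.5%

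If the true rates were 20% (already started) and 10% (new), about 8% of go results would show a Fisher p below 0.05 in that direction.

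**The case for a change.** The facts behind the worry are right. Two entry groups are admitted without a cap, one rule covers both, and the split by number of prior endocrine therapies is no substitute for fulvestrant status. The 10% is stated without derivation. A prespecified table would cost little and would carry more weight than one chosen after the result. Small cells did not deter the sponsor elsewhere: AR-negative results are planned although section 1.4 expects fewer than 10% AR-negative patients, fewer than 2.4 of 24.

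Some of this stands. A single-arm trial cannot separate enzalutamide from fulvestrant, and the observed rate belongs to the mix actually enrolled. A report that states how many patients were already on fulvestrant is easier to read.

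It does not make the plan deficient. The AR split serves a stated objective (section 1.4). The fulvestrant split would be one of several reasonable additions. It would not isolate enzalutamide either, because new starters begin both drugs together. With 24 patients, the collected treatment history and the planned listings should let a reader see where the patients with benefit fall, provided that the fulvestrant start date is recorded. Section 2.2 does not say when the 24 weeks of clinical benefit begin, but that is a matter for the endpoint definition and does not depend on pooling.

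**Conclusion.** The concern does not hold. The rule asks whether the combination's pooled clinical benefit rate in the eligible population exceeds 10%. Pooling the two entry groups answers that question, and it did not raise the error rate in the case checked with the pooled rate at 10% (0.082 against 0.085). The larger go probabilities, such as 0.285 or 0.414, arise only if the pooled rate is itself 15% or 17.5%. They rest on assumed shares and rates that the documents do not give, and the effect could equally be zero or in the opposite direction. Calling them false-positive rates would require 10% to be a fulvestrant-alone benchmark, which the plan does not state. A table by fulvestrant status would be an optional reporting extra: it changes neither n, nor the threshold, nor the decision, and it could seldom distinguish clustering from chance.
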